O0958-M

Treatment of Emotional Prosodic Disorders in
Parkinson's Disease

NCT01956266

August 11, 2014

Statistical Analysis Plan

Power analysis A sample power analysis using G*power (Erdfelder et al., 1996), and using an effect size from this treatment protocol in stroke with an alpha level of .05, power of .80, 1 group, indicated that we needed to recruit at least 24 participants to detect a small to medium effect size. As mentioned above, there is currently no data on means or standard deviations for these treatments within a Parkinson's disease population.

We propose to recruit approximately 24 participants for during the span of the CDA1 to serve as pilot data for treatment feasibility, treatment effect, and test-retest reliability for the primary outcome measure. Of this 24, we expect approximately half to receive treatment and half to participate only in test-retest reliability testing. The resulting data will be used for a power analysis based on means and standard deviations in PD to provide the number of subjects we will need to treat in subsequent studies.

Primary outcome measure - determine treatment effect size by comparing changes in acoustic variability. Affective sentence production. A list of 96 semantically neutral sentences of between five to seven words, spoken in one of four emotional tones of voice (24 each of happy, sad, angry and fear), presented in randomized order, will be administered before initiating treatment, after treatment is commenced, and at one month post treatment commencement. All sentences will be rated acoustically and perceptually. Repeated measures ANOVAS (or nonparametric equivalents) will be used to compare on the primary measure of acoustic variability: (a) pitch of frequency variability, and (b) intensity or loudness. If measurement time is a significant predictor of Fo range at a .05 Type I error level, we will use Tukey's method for pairwise comparisons to maintain the Type I error at .05 while performing post-hoc t-tests to determine which time point means are significantly different. As a secondary manner of analyzing this data if acoustic measures do seem not seem to have adequately captured any change, the prosodic expression outcome measure will also be perceptually rated offline by three trained judges who will rate the type of prosody and the intensity of emotional expression (0-5). The blinded judges for these and subsequent evaluations will be trained in evaluating the prosody of emotionally intoned sentences. Training for these judges will include familiarization with the descriptions of features for each emotion with respect to changes in pitch, loudness, and rate. Both intra- and inter-judge reliability will be calculated for these blinded judges.

Secondary outcome. Performance on identification, discrimination, and naming of facial and prosodic expressions of emotion. These will be assessed using the FAB before and right after treatment. Paired samples t-tests were used to compare performance on standardized tasks of affect recognition before and immediately following treatment.

Intra- and Inter-Judge Reliability. To evaluate intra-judge (test-retest) reliability, we will calculate mean and standard deviation of differences in the three perceptual outcome measures between the first and the second administration. Furthermore, we will calculate an intraclass correlation coefficient (ICC) estimate as well as a 95% confidence interval for ICC. In addition, ICC and related 95% confidence interval will also be calculated for inter-judge reliability at the first and the second administration, separately

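### The 80% power is attached to 24 participants, but only about 12 will be treated, so the treatment-effect analysis has roughly 46–47% power for the same effect

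*SAP*

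**What the plan says.** Under Power analysis, the SAP reports a calculation "using an effect size from this treatment protocol in stroke", "with an alpha level of .05, power of .80, 1 group", which "indicated that we needed to recruit at least 24 participants to detect a small to medium effect size". It gives no numeric effect size, effect-size metric, sidedness or within-person correlation. It adds that "there is currently no data on means or standard deviations for these treatments within a Parkinson's disease population".

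The next paragraph of that section takes about 24 as the recruitment target, calls the results pilot data, and says of the 24 that "we expect approximately half to receive treatment and half to participate only in test-retest reliability testing".

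Under Primary outcome measure, the sentence-production task is given "before initiating treatment, after treatment is commenced, and at one month post treatment commencement". Acoustic variability is compared over these three occasions by repeated measures ANOVA or a nonparametric equivalent, with time tested at the .05 level.

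**The concern.** The power calculation and the allocation of participants use the same number for different things. A one-group calculation of 24 means 24 people who each contribute a change over the treatment period. People who take part only in reliability testing receive no treatment, so they cannot contribute to that change. The analysis the power statement is meant to support therefore has about 12 people.

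At stake is how the result is read. The stated primary purpose is to determine the treatment effect size, and time is tested at .05. A reader who believes the study had 80% power for a modest effect may take a non-significant time effect as evidence against one, when the treated group had about an even chance, or slightly less, of detecting it.

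**Working it through.** **Inputs from the SAP.** Alpha .05, power .80, one group, N = 24 (Power analysis); about half treated, so 24 / 2 = 12 (same section); three occasions, repeated measures ANOVA (Primary outcome measure).

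**Assumptions, not in the SAP.** Two-sided test unless noted; within-person correlation ρ varied from 0.3 to 0.8; sphericity; conventional benchmarks of 0.2 and 0.5 for small and medium d, and 0.10 and 0.25 for f.

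**Step 1. The plan's own figure.** The number 24 can be neither reproduced nor refuted, because the effect size, its metric and the correlation are not given. Several inputs return about 24: dz = 0.60 in a two-sided paired test (power 0.804), or f = 0.25 with three occasions and ρ about 0.56. None can be identified as the one used.

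**Step 2. The same effect at 12.** This step needs no effect-size label and no value of ρ.

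- *Paired test.* Noncentrality δ = dz·√n, with n − 1 degrees of freedom. At n = 24, 80% power needs dz = 0.597, so δ = 0.597 × √24 = 2.93. At n = 12 the same dz gives δ = 0.597 × √12 = 2.07 on 11 df, and power 0.47. A one-sided test gives 0.52.
- *Three-occasion ANOVA.* Noncentrality λ = f²·n·m / (1 − ρ), with m = 3 and df = 2 and 2(n − 1). At n = 24, 80% power needs λ = 10.29. Halving n halves λ to 5.15, with df = 2 and 22, and power is 0.46. Because f and ρ enter only through λ, this holds for every ρ.

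**Step 3. What 12 can detect with 80% power.**

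- *Paired test.* dz = 0.889 two-sided (0.766 one-sided).
- *Three-occasion ANOVA.* λ must reach 11.08, so f = √(11.08 × (1 − ρ) / 36):

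| ρ | f at n = 12 | f at n = 24 (reference) |
|---|---|---|
| 0.3 | 0.46 | 0.32 |
| 0.5 | 0.39 | 0.27 |
| 0.7 | 0.30 | 0.21 |
| 0.8 | 0.25 | 0.17 |

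**Step 4. Correlation needed for the label to hold.**

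| Target f | ρ needed at n = 24 | ρ needed at n = 12 |
|---|---|---|
| 0.25 (medium) | 0.56 | 0.80 |
| 0.175 (midpoint of small and medium) | 0.79 | 0.90 |

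Departure from sphericity makes this worse. At n = 24 and ρ = 0.5, detectable f rises from 0.27 to 0.30 at ε = 0.75 and 0.34 at ε = 0.5.

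**The case against.** A reader might infer something stronger: that the label is simply wrong even for 24, since a paired test at 24 reaches 80% power only at dz = 0.60, above the usual medium value of 0.5. The documents do not support that. dz already absorbs the correlation, and the SAP does not say that its effect size is on that scale. In units of the score's standard deviation, with equal variances, d = dz·√(2(1 − ρ)). At 24 and ρ = 0.7 that is 0.597 × √0.6 = 0.46, below medium. On the planned ANOVA, f is 0.21 at ρ = 0.7, between small and medium. Nothing in the SAP rules out such a correlation for the same speaker producing the same sentence list. Nor can dz = 0.60 be presented as the sponsor's input; it is only one value that returns 24.

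It is also fair to say that this is a pilot, and that the SAP will size later studies from means and standard deviations observed in Parkinson's disease. It would therefore be wrong to claim that later studies inherit the present effect-size label. The missing inputs may stand in a protocol that is not at hand, and their absence alone would be a matter of detail.

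These points limit the consequence and remove the charge of an arithmetic error at 24. They do not touch the mismatch between 24 and about 12, which lies within one section of the SAP and needs neither a benchmark nor an assumed correlation.

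**Conclusion.** The stated power does not apply to the treatment-effect analysis. With about 12 of 24 treated, power for whichever effect had 80% at 24 falls to about 46% (planned ANOVA) or 47% (two-sided paired test). This rests on the SAP's own split, taken as exactly 12, on complete data and, for the ANOVA, on sphericity; on a one-sided reading it would be 52%.

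Whether the effect detectable at 12 counts as small to medium depends on the correlation. It does not at 0.7 or below (f of 0.30 or more), it just reaches medium at about 0.80, and it reaches the midpoint f = 0.175 only at about 0.90. At 24 the label is unsupported for want of a stated correlation, but not shown to be false. The matter is worth correcting because the SAP claims a property that the design lacks; its weight is moderate because the study is described as a pilot.

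**What to change.** In the Power analysis section, replace the small-to-medium claim with the effect detectable at 80% power in the number to be treated, under the planned analysis. Possible wording: *About 12 participants will be treated. With three occasions, alpha .05 and sphericity, a repeated measures ANOVA in 12 participants has 80% power for f of about 0.46, 0.39, 0.30 and 0.25 at within-person correlations of 0.3, 0.5, 0.7 and 0.8. For reference, 24 treated participants would give 0.32, 0.27, 0.21 and 0.17.*

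Beside this, record the numeric effect size taken from the stroke work, its metric and the correlation that were actually used to reach 24. Do not fill these in by working backwards, and do not attribute dz = 0.60 to that calculation.

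This changes wording only. It needs no extra enrolment and no change to the analysis. The only cost is a less favourable stated sensitivity.

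### The 80% power is calculated for 24 people in one group, but only about 12 will be treated; for the same effect, power falls to a little under half and is not restated

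*SAP*

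**What the plan says.** All of the sample-size text is in the SAP's Power analysis section.

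- The calculation was run in G*Power "using an effect size from this treatment protocol in stroke", with "alpha level of .05, power of .80, 1 group", and it "indicated that we needed to recruit at least 24 participants to detect a small to medium effect size".
- The next paragraph recruits approximately 24 people "to serve as pilot data for treatment feasibility, treatment effect, and test-retest reliability for the primary outcome measure". It then divides them: "Of this 24, we expect approximately half to receive treatment and half to participate only in test-retest reliability testing".
- Looking ahead, "The resulting data will be used for a power analysis based on means and standard deviations in PD", to set the number to treat in later studies.

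The Primary outcome measure section states its aim as "determine treatment effect size by comparing changes in acoustic variability". The sentence list "will be administered before initiating treatment, after treatment is commenced, and at one month post treatment commencement", and time is tested by repeated measures ANOVA (or a nonparametric equivalent) at the .05 level before any pairwise comparison.

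The SAP gives no power, detectable effect or precision for the half who are treated.

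**The concern.** The number 24 is used in two senses. In the calculation it is the size of a single group whose treatment effect is to be detected; an effect size taken from the treatment protocol can only describe treated people. In the recruitment paragraph it is the total enrolled, about half of whom never receive the treatment. Those in the test-retest half take part only in that testing, so they cannot contribute to a comparison of before, after and one month after the start of treatment.

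Two things are at stake. First, the power paragraph is the SAP's only statement of what the study can detect, and it describes about twice as many treated people as are planned. Someone who takes 80% at face value would give a non-significant test of time more weight than about 12 people can support. Second, the results are meant to size later studies, and the treatment-change estimate carried forward would come from about 12 people.

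**Working it through.** **Inputs from the SAP.** Alpha .05, power .80, one group, at least 24 required (Power analysis); about half of about 24 treated, so n ≈ 12 (Power analysis); three measurement times and a repeated measures ANOVA (Primary outcome measure).

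**Not given.** Numerical effect size, the test used in the power run, sidedness, within-person correlation. The 24 can therefore be neither confirmed nor refuted. It is attainable: a three-time ANOVA with f = 0.27 and an assumed correlation of 0.5 gives 24, and so does a two-sided paired t-test with d = 0.6. The check takes 24 as correct, solves for the effect it implies, holds that effect fixed and recomputes power at the treated number.

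**Three-time repeated measures ANOVA, one group.** Noncentrality λ = n·3·f²·ε/(1−ρ), with 2ε and 2(n−1)ε degrees of freedom. Here f is the effect size, ρ the within-person correlation and ε the sphericity factor.

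- Check of the formula: f = 0.25, ρ = 0.5, n = 28, ε = 1 gives 81.2% power.
- n = 24, ε = 1: critical F(2, 46) = 3.200. Power of .80 requires λ = 10.29, or 10.29/24 = 0.4288 per person.
- n = 12, same effect: λ = 12 × 0.4288 = 5.145; critical F(2, 22) = 3.443; **power = 45.9%**.
- ρ enters only through the per-person noncentrality, which the anchor fixes, so it cancels.
- Without sphericity, n = 12 gives 46.5% (ε = 0.75), 46.8% (ε = 0.6) and 47.1% (ε = 0.5).

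**Paired t-test.** Noncentrality d√n, with n−1 degrees of freedom.

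- Two-sided: 80% at n = 24 requires d = 0.597. At n = 12 the noncentrality is 0.597 × √12 = 2.069 against a critical value of 2.201; **power = 47.1%**.
- One-sided: 80% at n = 24 requires d = 0.523. At n = 12 the noncentrality is 1.812 against 1.796; power = 52.2%.

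**Sensitivity to the number treated.** The SAP says only approximately half, with the same effect held fixed:

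| Treated | ANOVA (ε = 1) | Paired t, two-sided | Paired t, one-sided |
|---|---|---|---|
| 10 | 38.1% | 39.3% | 45.4% |
| 11 | 42.1% | 43.3% | 48.9% |
| 12 | 45.9% | 47.1% | 52.2% |
| 13 | 49.7% | 50.8% | 55.3% |
| 14 | 53.2% | 54.3% | 58.3% |

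**Sensitivity to rounding.** If 24 was rounded up from just over 23, the implied effect is slightly larger. Power at 12 is then at most 47.8% (ANOVA, ε = 1), 48.9% (two-sided t) or 53.7% (one-sided t).

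**Detectable effect.** For 80% power with 12 treated, the two-sided paired t-test needs d = 0.889, and 0.889/0.597 = 1.49 times the effect detectable with 24. For the ANOVA under sphericity the ratio is 1.47.

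**Precision.** The 95% confidence interval half-width for a mean change, in units of the SD of change, is t(.975, n−1)/√n:

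- n = 12: 2.201/√12 = 0.635
- n = 24: 2.069/√24 = 0.422
- Ratio 0.635/0.422 = 1.50, that is, 50% wider.

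**The case against.** The strongest reply is that nothing is hidden. The split is stated shortly after the calculation, the sample is called pilot data, the SAP admits there are no means or SDs in Parkinson's disease, and the declared aim is to determine an effect size and then power later studies. The plan never says outright that the treated group has 80% power. On this view the defect is an inference from two adjacent paragraphs, and an interval from 12 people is the known limit of a pilot.

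Much of this is fair, and it is why no extra enrolment is asked for. It does not settle the point. The 80% calculation is presented as the basis for recruiting 24, that same number is then recruited, and no sentence says that the calculation fails to describe the treated half. The primary analysis also remains a test at .05.

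Some narrower objections stand in part:

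- No arithmetic in the SAP is shown to be wrong; the 24 is simply not reconciled with the number treated.
- A figure of 46–47% is conditional on an F test or a two-sided t-test and on exactly 12 treated. The table in the working shows the wider range.
- Missing an effect about half the time refers to a single test. The SAP names two acoustic measures and does not say which outcome the stroke effect size came from.
- The SAP does not propose to conclude no effect from a non-significant result, so advice on interpretation and on emphasising the interval is secondary to restating the power.

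**Conclusion.** The point holds and should be fixed. The SAP's 80% power belongs to 24 treated people in one group; about 12 are planned, and the figure is not restated for them. For the effect that 24 would detect with 80% power, 12 treated give about 46–47% with the planned ANOVA or a two-sided paired t-test, and about 52% with a one-sided t-test. No variant examined, with 10 to 14 treated, exceeds 58.3%.

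The result assumes that 24 was right for the sponsor's own inputs and that the test-retest half contributes nothing to the treatment comparison, which is what the SAP says. It needs neither the unstated effect size nor the correlation, since both are absorbed when the effect is tied to 24.

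**What to change.** Rewrite the power paragraph for the number actually treated:

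- State that the calculated 24 refers to treated participants in one group, that about 12 are expected to be treated, and that the rest inform test-retest reliability only.
- Re-run the sponsor's G*Power calculation at n = 12. Report its inputs (effect size, test, sidedness, correlation), the resulting power and the effect detectable with 80% power.
- Remove the implication that the treated group has 80% power for a small-to-medium effect.
- As a secondary change, and in keeping with the stated pilot aim, present the estimated change with its 95% confidence interval as the main result. Say that a non-significant test will not be read as evidence of no effect.

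The cost is a few sentences in the SAP and one repeat of an existing calculation. Enrolment, endpoint, test and data collection stay as they are. The stated power becomes less favourable.

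### In its usual complete-case form, the planned three-occasion ANOVA drops anyone who misses a session; with about 12 treated, a mixed model is a cheap improvement

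*SAP*

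**What the plan says.** All of this is in the SAP.

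- **Aim (Primary outcome measure):** "determine treatment effect size by comparing changes in acoustic variability".
- **Occasions (same paragraph):** the sentence list "will be administered before initiating treatment, after treatment is commenced, and at one month post treatment commencement", which makes three.
- **Method:** "Repeated measures ANOVAS (or nonparametric equivalents) will be used to compare on the primary measure of acoustic variability". If time is significant at the 5% level, "we will use Tukey's method for pairwise comparisons to maintain the Type I error at .05 while performing post-hoc t-tests".
- **Number treated (Power analysis):** of about 24 recruited, "we expect approximately half to receive treatment and half to participate only in test-retest reliability testing", so about 12 people contribute to the treatment analysis.
- **Use of the result (Power analysis):** the observed means and standard deviations in Parkinson's disease will set the size of later studies.

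The SAP does not say how a missed session is handled, and does not say whether the pairwise tests use only people with all three recordings or every available pair.

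**The concern.** Classical repeated measures ANOVA and the Friedman test both need a value from each person at each occasion. Someone with recordings before and after treatment but none at one month has a complete pre-post pair, yet contributes nothing to the omnibus test. If the Tukey comparisons come from that fit, the pair is lost there too.

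With about 12 treated, each lost person is 1/12, or about 8%, of the sample. Two things are at stake. One is the precision of an effect size that is the declared product of the study. The other is selection: if people who respond poorly are less likely to come back, completers overstate the effect, and the next study, sized on that value, would be too small.

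**Working it through.** **The plan's own figure.** The Power analysis gives 24 participants, "with an alpha level of .05, power of .80, 1 group", "using an effect size from this treatment protocol in stroke". No numeric effect size is printed, so 24 cannot be reproduced. It is consistent with a two-sided paired test at a standardised change (dz) of 0.60, which needs 24 pairs. The dz below is borrowed from that match and is an assumption.

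**Inputs.** From the SAP: about 12 treated, three occasions, alpha 0.05. Assumed: the number lost, the rate of missed sessions, and how far missingness depends on response.

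**1. How likely is an incomplete record?** Let each of the two post-baseline sessions be missed independently with probability p. The expected number complete is 12(1−p)², and the chance of at least one incomplete person is 1−(1−p)²⁴.

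| p | expected complete of 12 | chance of at least one incomplete |
|---|---|---|
| 5% | 10.8 | 71% |
| 10% | 9.7 | 92% |
| 20% | 7.7 | over 99% |

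**2. Precision of the pre-post change.** The 95% half-width, in SDs of the change, is t(0.975, n−1)/√n. Power is for a two-sided paired t-test at dz = 0.60 (noncentral t, noncentrality 0.60√n).

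| n | half-width | ratio to n = 12 | paired power |
|---|---|---|---|
| 12 | 2.201/√12 = 0.635 | 1.00 | 47% |
| 11 | 2.228/√11 = 0.672 | 1.06 | 44% |
| 10 | 2.262/√10 = 0.715 | 1.13 | 40% |
| 9 | 2.306/√9 = 0.769 | 1.21 | 35% |

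**3. The omnibus test itself.** Use the noncentral F with λ = f²·n·3/(1−ρ) and degrees of freedom 2 and 2(n−1), sphericity assumed. At the f that gives 80% power with 24 people (0.267 if ρ = 0.5), power is 46% with 12, 38% with 10 and 34% with 9. These three values do not depend on ρ, because f is rescaled to match.

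**4. Bias among completers.** Let the pre-post change have mean 0.60 and SD 1, and let 20% miss the one-month session. The log-odds of missing fall by b per SD of observed change.

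| b | odds ratio per SD of poorer response | completers' mean change |
|---|---|---|
| 0 | 1.00 | 0.60 |
| 0.25 | 1.28 | 0.65 |
| 0.5 | 1.65 | 0.70 |
| 1.0 | 2.72 | 0.77 |
| 1.5 | 4.48 | 0.83 |
| 2.0 | 7.39 | 0.86 |

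If exactly the worst 20% were lost, the completers' mean would be 0.95, the ceiling at this rate.

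**5. What a mixed model recovers.** If only one-month recordings are missing, the pre-post estimate from a model with free means at each occasion equals the mean change over all 12. Simulation with 12 people, correlation 0.6, a true change of 0.50 and a random-intercept REML fit agrees. With about 20% missing at random, the pre-post standard error was 0.282 for complete cases and 0.252 for the mixed model, with no bias in either. With strong dependence on early change (about 3 of 12 missing), complete cases gave 0.76 and the mixed model 0.50. Some fits at this size gave convergence warnings.

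**The case against.** The strongest reply is that the SAP never says incomplete cases are dropped. A reader might infer that the plan discards the pre-post data of anyone who misses the one-month session. The text does not support that: it calls for post-hoc t-tests, and t-tests on available pairs would keep such a person. This stands, and the pre-post loss is therefore conditional. The omnibus test is still affected in its usual form, and the pairwise tests are reached only if that test is significant.

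Second, the harm needs missed sessions. Follow-up is short, the SAP gives no attrition figure, and the protocol, which was not available for this check, may deal with retention and missed visits. This stands as a limit on size. It does not change how the named method treats incomplete records, and choosing the primary analysis method is the SAP's own business.

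Third, the 0.83 scenario is steep: about 40% would be missing at 1 SD below the mean change against about 3% at 1 SD above. A reader might take inflation of that order as expected. Nothing in the SAP supports that, and only the range, which starts at no bias, can be defended.

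Fourth, the plan specifies no confidence interval for the primary effect, no stand-alone paired test and no dz. The interval widths therefore measure the precision of the effect size and not a planned output; step 3 of the working gives the loss for the planned test.

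Fifth, an unstructured covariance fitted to about 12 people is fragile. This stands, and any replacement wording needs a named fallback.

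**Conclusion.** The point holds in conditional form and as a suggested improvement (CONSIDER). Under the usual complete-case implementation, a treated participant with one missed session leaves the omnibus test, and leaves the pre-post comparison too if the pairwise tests use the same set.

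- **Precision:** losing 1 to 3 of 12 widens the pre-post interval by 6% to 21%.
- **Bias:** with 20% missing the one-month session in a way that depends on the pre-post change, 0.60 SD becomes about 0.65 to 0.86. It stays at 0.60 if missingness is unrelated to response.
- **No missed sessions:** nothing is lost.

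Every missingness rate and dependence strength here is assumed. The scenarios let missingness depend on observed values, which is the condition under which a mixed model is valid; it would not remove bias if absence depended on unobserved outcomes. It also recovers little about the pre-post change from someone whose pre or post recording is itself missing. A reader might go further and call the primary analysis invalid or its effect size necessarily inflated. The SAP supports neither.

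**What to change.** Replace the method sentence under Primary outcome measure with wording such as:

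*Each acoustic measure will be analysed with a linear mixed model fitted by REML to all available recordings from treated participants, with occasion as a categorical fixed effect, an unstructured covariance across the three occasions and Kenward-Roger degrees of freedom. If this model does not converge, a compound-symmetry (random-intercept) covariance will be used. Tukey-adjusted pairwise contrasts between occasions will be taken from the fitted model. Validity assumes that data are missing at random.*

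The cost is SAP wording and standard software. With complete data, the unstructured model's contrasts, before Tukey adjustment, reproduce the paired comparisons, so little is given up, and the sphericity assumption of the ANOVA is no longer needed. The downsides are possible non-convergence with about 12 people and, under the fallback, the return of a sphericity-type assumption.

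### Perceptual rating is promised for all sentences but also made conditional on an undefined, one-way look at the acoustic result

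*SAP*

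**What the plan says.** The Primary outcome measure paragraph sets the acoustic aim, to "determine treatment effect size by comparing changes in acoustic variability", and names two acoustic measures, pitch variability and intensity. Four statements bear on the perceptual ratings:

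- Without condition: "All sentences will be rated acoustically and perceptually".
- With a condition: "As a secondary manner of analyzing this data if acoustic measures do seem not seem to have adequately captured any change", then "the prosodic expression outcome measure will also be perceptually rated offline by three trained judges". The judges rate the type of prosody and the intensity of expression.
- Without condition, later in the same paragraph: intra- and inter-judge reliability will be calculated for the blinded judges.
- Without condition, under Intra- and Inter-Judge Reliability: means and standard deviations of "differences in the three perceptual outcome measures between the first and the second administration", with intraclass correlations and 95% confidence intervals.

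No model, test or alpha is given for perceptual change over time.

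**The concern.** Two people following this plan after a clearly positive acoustic result could properly do different things. One would rate every sentence and report perceptual change; the other would see no call to. After a null or doubtful acoustic result, someone who has already seen that result must decide whether it amounts to a failure to capture change, and the plan gives no rule for deciding.

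The condition also runs in one direction. Perceptual evidence is sought as a remedy for a disappointing primary result, never as a check on a favourable one. Two things are at stake: a second opportunity to claim change once the first has failed, and a reported perceptual effect that comes only from pilots selected by their acoustic result.

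**Working it through.** **1. The text.** Grammatically, the condition attaches to the rating itself. That contradicts the statement that all sentences will be perceptually rated, and it contradicts both reliability statements, which need ratings to exist. If the condition is taken to cover only the analysis, that contradiction eases, but the analysis still depends on how the primary result looks.

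**2. Is the trigger defined?** The same paragraph does define another gate, the one for the Tukey comparisons: "If measurement time is a significant predictor of Fo range at a .05 Type I error level". The perceptual clause has no counterpart. It gives no p-value, effect size, time contrast or decision-maker, and does not say whether one or both acoustic measures must fail. Correcting the garbled verb does not supply any of these.

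**3. How much the reading matters (illustration).** The SAP states no effect size in Parkinson's disease, no correlation between measures and no perceptual test. Assumptions:

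- n = 12 treated (about half of the 24 in the Power analysis paragraph);
- the same true standardized paired change d on pitch, intensity and one perceptual measure;
- a common correlation r;
- two-sided .05 paired t-tests, with p ≥ .05 standing in for the undefined trigger.

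Power of one acoustic test is P(|T| > t(.975, 11)), where T is noncentral t with 11 df and noncentrality d√12. This gives 0.097, 0.35 and 0.71 at d = 0.2, 0.5 and 0.8. At r = 0 and d = 0.5, both tests are null with probability (1 − 0.352)² = 0.42, and at least one is null with probability 1 − 0.352² = 0.88. Simulation (200,000 replicates per cell) gives the share of pilots in which the clause fires, for r from 0 to 0.9:

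| d | both null | pitch null | either null |
|---|---|---|---|
| 0.2 | 82–87% | 90% | 94–99% |
| 0.5 | 42–57% | 65% | 72–88% |
| 0.8 | 8–22% | 29% | 35–49% |

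A repeated-measures ANOVA version at d = 0.5 (three time points, sphericity, change held after treatment) gives 40–56%, 63% and 71–87%.

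**4. Selection.** Mean observed perceptual d when analysed only after a null pitch result:

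| true d | r = 0 | 0.3 | 0.6 | 0.9 | always analysed |
|---|---|---|---|---|---|
| 0.2 | 0.22 | 0.20 | 0.18 | 0.17 | 0.22 |
| 0.5 | 0.54 | 0.49 | 0.43 | 0.37 | 0.54 |
| 0.8 | 0.86 | 0.75 | 0.63 | 0.50 | 0.86 |

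The comparator is the last column, not the true d. At n = 12 the observed d averages about 1/(1 − 3/43) = 1.075 times the true value (0.5 × 1.075 = 0.54). Selection has no effect at r = 0 and lowers the mean when r is positive.

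**5. Second chance.** With no true change and each test at two-sided .05, one acoustic test followed by one perceptual test if null gives at least one positive with probability 1 − 0.95² = 0.0975 if independent, falling to 0.078 at r = 0.8, against 0.05 for the acoustic test alone. Two acoustic then two perceptual tests give 1 − 0.95⁴ = 0.186 if independent and 0.114 at r = 0.8, against 0.098 and 0.078 for the two acoustic tests alone. The number of perceptual tests is an assumption.

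**The case against.** The strongest reply is that three unconditional statements outweigh one loose clause, so the ratings will exist and only their use as a fallback analysis is conditional. That is a fair reading, and part of it stands. A reader might infer that a positive acoustic pilot would have no perceptual data at all. The SAP does not support that, because the sentence on rating all sentences and both reliability plans say the ratings will be made. What is missing after a positive result is a planned analysis of perceptual change. The undefined trigger remains on either reading.

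The figures also have limits. The clause may refer to the acoustic measures being insensitive rather than to a non-significant test, so p ≥ .05 is a stand-in, and the shares vary strongly with the assumed d. The false-positive figures matter only if a positive perceptual result is read as a treatment effect.

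A reader might further infer that a selected perceptual effect would distort the next study's sample size. The Power analysis paragraph says only "The resulting data will be used for a power analysis based on means and standard deviations in PD" and names no measure, while the stated effect-size aim is acoustic. That route is possible but not stated, and the point does not rest on it.

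Finally, two perceptual ratings are named under the primary outcome and three under reliability. A third may be defined in the protocol, which is not at hand. This should be reconciled but adds no weight here.

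**Conclusion.** The point holds on the text alone. The SAP contradicts itself on whether perceptual rating is conditional. On any reading it makes the perceptual analysis depend on an undefined, one-way judgement taken after the primary result is known.

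Under the assumptions above, at d = 0.5 the clause could fire in anything from 42% to 88% of pilots. The mean perceptual effect reported after a null pitch result would be lower than if always analysed by 0.05 (0.54 − 0.49) at r = 0.3 and by 0.17 (0.54 − 0.37) at r = 0.9, with no difference at r = 0. These figures illustrate the mechanism; the SAP supplies neither d nor r.

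The weight is modest: it should be corrected, at the lower end of that grade. The analysis is secondary, the study is a pilot, the judges are blinded and the primary acoustic test is untouched.

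**What to change.** Delete the conditional clause in the Primary outcome measure paragraph and say instead: *Perceptual ratings of all sentences by the three blinded judges are a prespecified secondary analysis, carried out and reported whatever the acoustic result; they do not replace the acoustic primary outcome.* This removes the contradiction, the undefined trigger and the selection together. In the same edit, make the number of perceptual measures agree with the Intra- and Inter-Judge Reliability paragraph.

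The cost is wording only if all sentences are rated as the SAP already states. If they would otherwise not be rated, the work for the treated participants is about 12 × 96 sentences × 3 time points × 3 judges = 10,368 sentence-by-judge presentations. With two ratings each, that is 20,736 ratings. Repeat ratings for intra-judge reliability come on top. So would the test-retest sentences, if rated: assuming 12 participants and two administrations, 12 × 96 × 2 × 3 = 6,912 presentations.
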